Protocol cover sheet

Wearable Dark-adaptometer in Normal Adult Healthy Volunteers

NCT number NCT02674425

Version 2.0 27/01/2017

WONDER STUDY
Evaluation of a novel wearable light-emitting system for measuring dark-adaptation thresholds in normal adult healthy volunteers

STUDY PROTOCOL

Chief Investigator: [name]
Principal Investigator: [name]
Co-Investigator: [name]
Collaborator: [name]

Clinical Eye Research Centre, St Paul's Eye Unit, Royal Liverpool University Hospital, [name]
University of Liverpool, Department of Eye and Vision Science, Institute of Ageing and Chronic Disease, [name]

Contents

- 1. Project summary**
- 2. Background**
- 3. Aims**
- 4. Methods**
 - 4.1. Study design
 - 4.2. Setting
 - 4.3. Investigational system
 - 4.4. Participants
 - 4.5. Inclusion criteria
 - 4.6. Exclusion criteria
 - 4.7. Procedures
 - 4.8. Detailed description of investigations
 - 4.9. Study schedule
 - 4.10. Recruitment
 - 4.11. Primary outcomes
 - 4.12. Secondary outcomes
 - 4.13. Data collection/Project management
 - 4.14. Data analysis
 - 4.15. Adverse event management
 - 4.16. Study personnel
- 5. References**
- 6. Dissemination**

1. Project Summary

Aim:

- Assess the dark-adaptometry testing performance of a novel wearable light-emitting system by generating full dark-adaptation threshold functions in normal adult healthy volunteers

The study intends to answer the following research questions:

- Is it possible to reproduce state-of-the-art threshold measurements as good or better than those produced by commercially-available dark-adaptometers and reported in the literature?
- Do the threshold measurements in the elderly compare with literature data adjusted to exclude aged crystalline lens and pupillary miosis contributions?
- Are test results from the wearable light-emitting system repeatable?
- If the results are not repeatable, can any assumption be made about reducing their variability through software and/or hardware optimisation of the novel light-emitting system?
- Is the novel light-emitting system comfortable and easy to use by normal healthy adults despite age differences?

Study design:

- Single-centre, observational healthy case-only study
- 20 healthy volunteers

Study investigations:

- General wellbeing
- Retinal structure, visual and behavioural test series
 - Refractive error
 - Distance Visual Acuity (DVA)
 - SKILL card
 - Contrast sensitivity
 - Pupillometry
 - Confrontational visual fields
 - Direct ophthalmoscopy
 - Psychomotor capability
- System performance
 - Dark-adaptometry testing
- System usability
 - Ad hoc pen-and-paper questionnaire

Results of the study will be publicised by papers submitted to international peer-reviewed journals and proceedings of international conferences.

2. Background

Human sensitivity to visible light is altered by the retina based on the surrounding illumination and varies with the state of adaptation of the observer. The eye becomes accustomed to a light brighter than the surrounding illumination it is exposed to through a process called light adaptation [1-2]. As the surrounding illumination decreases, the eye becomes accustomed to the lower light level through a process called dark adaptation [2-3]. Between the two extremes there is an infinite number of adaptation or threshold states [4].

The threshold luminance refers to the smallest difference between two light levels that can be distinguished by a subject. The threshold luminance is inversely proportional to the eyes' sensitivity: as the sensitivity of the retina increases the threshold decreases (i.e., a lower

luminance evokes a response); vice versa, as sensitivity decreases a brighter light is required to evoke a visual response in a subject and the threshold is raised. Thus, large changes in the ambient light level are required for the light-adapted eye to perceive any change; in contrast, the dark-adapted eye is extremely sensitive to light perceiving very small variations in the luminance [5-6].

In 1865, Aubert [7] first described the dark-adaptation process as an observable increase in sensitivity of the visual system to light when the ambient light level decreases. It is a common experience initially to find it difficult to see anything when entering a dimly light room from the sunny outdoors conditions. Indeed, the visual function restores gradually [2, 8] and the human eye safely adapts to extremes of bright and dark lighting conditions spanning a range of about $1 \times 10^{10}:1$ [9].

Dark adaptation primarily depends upon four processes: changes in pupil size, changes in the neural network, photochemical changes of the visual pigments, and changes in the calcium and sodium channels present in the photoreceptors [4, 8]. Certain eye diseases, inherited abnormalities, metabolic disorders and nutritional deficiencies may be identified by changes in dark-adaptation thresholds as determined by investigation of the dark-adaptation curve (i.e., repeated measurements of light threshold as a function of time). Dark adaptometers are instruments used to evaluate dark adaptation and are important in the diagnosis, prognosis and monitoring of identified symptoms including night blindness, retinal dystrophies, and hypovitaminosis A.

Measurement of dark adaptation typically involves the presentation of a light stimulus, which may comprise an ascending or descending threshold [10] (the staircase threshold method providing more accurate measurements). Tested subjects are asked to indicate when the stimulus appears or alternatively disappears [1, 11]. The time taken for the stimulus to become visible to the observer [12-13] is recorded. During a dark-adaptometry test the stimulus is always presented against a completely dark background field with the subject in complete darkness or blackout. At the start of the test the threshold luminance is initially high and decreases as one dark adapts.

The dark-adaptation curve is obtained by plotting a graph of each measured light threshold against the time [1, 14]. Each plotted threshold represents the time it takes the subject to perceive the light stimulus. A typical dark-adaptation curve is presented in Figure 1.

[figure not shown]

Figure 1. Normal dark-adaptation curve obtained using the Goldmann-Weekers adaptometer as a function of time. The discrete points are the recorded thresholds, whereas the best fit line identifies the dark-adaptation curve. The pre-adaptation light duration was 2 minutes at 1500 mL. (Figure reprinted from [15])

The typical range from highest threshold luminance to absolute rod threshold covers about 5 logarithm units of luminance [16]. The first part of the curve is the photopic phase, which identifies the cone adaptation. The last part of the curve is the scotopic phase, which identifies the rod adaptation [11]. The interval between the two phases is commonly referred to as the rod-cone break. It can be seen in Figure 1 that, as the luminance is reduced, there is an increase in light sensitivity, which is initially very rapid before levelling off after 5 to 10 minutes at the final or absolute cone threshold [5]. At this point, the foveal cone cells are fully dark adapted (i.e., they have reached their maximum sensitivity [17]); in contrast, the rod cells are saturated and inactive [1]. With time (the luminance of the stimulus is reduced) a second slower fall in the threshold luminance is observed as the peripheral rod cells become activated (rhodopsin is regenerated). Rod adaptation is slower than the cone adaptation [18] because of the regeneration half-life of the visual pigments. However, unlike cone cells, light of very low intensity is capable of stimulating the rod cells, when given sufficient time to accumulate rhodopsin [2]. After approximately 30-40 minutes in total darkness, the final rod threshold is achieved. Dark adaptation is now complete and no further increase in sensitivity of the rods photoreceptors is possible.

The time required to reach maximum sensitivity is dependent on the amount of pigment bleached by the previous light exposure [19] and neural adaptation. The wavelength of the incident light has also a strong influence on the dark-adaptation curve, given that cone mediated vision is responsible for colour vision whereas rod vision is colourless.

Both cone and rod dark-adaptation curves consist of an initial rapid nonlinear increase in sensitivity (i.e., the S1 component of recovery) followed by a second longer section (i.e., the S2 component of recovery) of near linear slope and a third section (i.e., the S3 component of recovery) where the curve asymptotically reaches the final cone and rod threshold, respectively [18]. The first section of the cone phase curve may be explained by the rapid increase in pupillary diameter [8, 20]. The near linear middle sections are determined by the regeneration of bleached visual pigments in the outer segment discs of the cone and rods [21]. The difference in the decay curve of both cone and rod mediated vision may be explained by different regeneration half-lives of the rod ($t_{1/2} = 5$ minutes) and cone ($t_{1/2} = 90$ seconds) cells thus cone pigments are regenerated at a faster rate than rhodopsin.

Despite the use of more objective modern instrumentation [22-23], the subjective determination of human dark adaptation has provided important information on the structure and functioning of the retina and continues to be a useful investigative tool.

Most dark adaptometers are based on the Hecht-Schlaer adaptometer developed in the 1938 [19], which is considered the first reliable instrument allowing for an accurate investigation of the various aspects of dark adaptation after previous attempts carried out by use of photometer devices [8, 15, 24]. Variation of the light stimulus was obtained by Hecht and Schlaer upon the insertion of several neutral density filters in front of a tungsten light source. The test field subtended 3° and was presented 7° nasally to the fixation light. The fixation intensity was adjustable and was maintained so as to be just visible by the subject throughout the test. Dark adaptation data obtained from this device under controlled conditions were accurate, reliable and reproducible. Many subsequent instruments are essentially modifications and improvements on this device [25-28]. A notable device was constructed by Wald [29] in 1941 and used to survey vitamin A deficiency in Newfoundland, but with limited success. A novel landmark, low cost instrument was developed by Henson and Allen [30] in 1977 consisting of a single stimulus of a green (565 nm) solid-state light-emitting diodes (LEDs) as opposed to tungsten filaments used in earlier devices. The stimulus intensity control setting was via a manual position switch that corresponded to 12 discrete luminance light levels that were approximately half (or a quarter) the previous presentation luminance. The fixation distance was 33 cm. Electronic circuitry controlled the LED light output to a quoted accuracy of 0.1%, which could be maintained over ten years of continuous use. A potential deficiency with this

instrument was that the test was self-administered/controlled leading to possible significant bias in the test results. In addition, it lacked a chin rest, thus the distance between the stimulus and the subject appears not to have been fixed; consequently, there is an uncertainty in the exact stimulus size and eccentricity to the fovea.

Particularly important is the Goldmann-Weekers adaptometer (Haag-Streit AG) [31]: an expensive, highly sophisticated and versatile instrument that has attained the status of the benchmark instrument by which other instruments past and present are compared and evaluated [32-37]. The instrument is still in use today but not commercially available any longer. It comprises an integrating sphere required for light adaptation and a chin rest that fixes the viewing distance. With the subject's head resting on the chin rest a single circular 11° target stimulus is located centrally and directly in front of the subject's eyes. A red fixation light is traditionally presented at 11°-15° to the fovea [6]. Newer models of Goldmann-Weekers adaptometer unit are available with a movable fixation light thus enabling examination of the full retina. The recording of the threshold luminance values is made by the operator activating a lever on a recording arm connected to an indicating "pricker" that perforates a logarithmic paper chart, which is mounted on a recording drum rotating once per hour.

Time is plotted on the abscissa in minutes while the luminance is plotted on the ordinate. Changes in stimulus luminance of both the target and fixation luminance are manually achieved. Up to 100 thresholds measurements are made until the threshold stabilises, typically after 30-40 minutes; the test is then terminated. The paper chart is removed and the best fit curve subjectively drawn by the operator through the series of perforations thus yielding the adaptation curve. A skilled and experienced operator must carry out the test in the dark along with the subject under examination throughout the test. A full description of the testing methodology is described by Russell et al. [10].

Field analysers may also be used to obtain dark adaptation measurements [38]. For example, a modified Friedmann field analyser described by Bedwell [39] has been used extensively to measure dark adaptation [40]. Neugebauer and Vemon [41] developed a dark adaptometer based on the Lister perimeter. This instrument was successfully used by Rayner and Tyrrell [40] to investigate nyctalopia in cystic fibrosis patients. The disadvantage of using field screeners and perimeters is that the instrumentation is not specifically designed for dark adaptation measurements; consequently they are of limited use compared to dedicated instrumentation such as the Goldmann-Weekers device.

However, there are significant disadvantages and limitations inherent in currently used dark adaptometers including:

- 1) the use of old and out dated technology;
- 2) most adaptometers are elaborate, large, heavy, non-portable and expensive;
- 3) test procedures require full attention of highly trained operators in a clinical environment;
- 4) electrical supply is provided by mains, thus making them immobile and unsuitable for field investigations;
- 5) the operator must carry out the test in total darkness with the subject under test;
- 6) test data acquisition is manually obtained by the operator;
- 7) data analysis is complex requiring additional operator time after the test has terminated;
- 8) frequently, only one area of the retina may be tested at any one time;
- 9) there is a test learning curve leading to the possibility of biased results.

The need for an entirely dark room is also a physical limitation and an economic burden for the use of most of the modern portable-adaptometer instruments such as the scotopic sensitivity tester-1 (SST-1) (LKC Technologies) and the AdaptDx (MacuLogix). The SST-1 instrument entered the market as an efficient device for quickly identifying night-blindness in patients with retinal degeneration. However, several drawbacks have been identified when testing with the SST-1 including: the narrow range of measurable intensities (3.0 logarithmic units); the too dim luminance at its maximum intensity in order to evaluate subjects who had severe scotopic

sensitivity losses (floor effect); the too bright luminance at its minimum intensity in order to evaluate thresholds in subjects with good scotopic sensitivity (ceiling effect); the non-adequate initial adapting light for photopigment bleaching. In addition to standard dark-adaptometry testing, the AdaptDx is claimed to allow for early AMD diagnosis but this use is to date restricted to research purposes only.

For the reason listed above, conventional dark-adaptometers are unsuitable as a mass screening tool; consequently, dark adaptation is not routinely used as a clinical technique because of the practical problems it presents [33, 39-42].

In order to overcome the associated problems with current instrumentation described above, the use of a novel, wearable and semi-automated dark-adaptometer is proposed. This is implemented as a pair of head-mounted googles and a handheld joystick, and it is easy to use without the need of any skilled operator. The novel dark-adaptometer is very versatile, uses low-cost solid-state electronics, and features low-power consumption, which allows for battery-powered operation. For a more comfortable user experience, the system is light and characterised by durable enclosures that totally black-out the inside of the goggles, hence avoid the need of a dark room to carry out dark-adaptometry testing.

The portability, ease of use, and relatively low cost of this system aims to spread the practice of dark-adaptometry testing and let it be adopted also by high-street optometrists. This will allow diagnosing a number of retinal pathologies more quickly and more reliably eventually bypassing the use of other visual electrophysiology equipment such as the ERG system: a more expensive instrument characterised by a larger form factor and a range of features that may be surplus to optometrists' requirements. Receiving a quick diagnosis may lead to starting a treatment sooner; faced with an ageing population, this represents a major asset to the Health Community and the NHS.

The wearable light-emitting system as described can represent a viable diagnostic tool for measuring dark-adaptation thresholds with proven good reproducibility and precision of the test data when compared to conventional instrumentation. Since the intensity, duration, colour, area and location of the light used for the fixation, bleach, and target stimuli all have an influence on the measured thresholds [8, 19, 44], the modified 3-down-1-up staircase procedure carried out in [43] will be adopted here for comparison purposes with data results reported in the literature.

3. Aim

The aim of this study is to assess dark-adaptometry testing performance of a novel wearable light-emitting system by generating full dark adaptation threshold functions in normal adult healthy volunteers.

The study intends to answer the following research questions:

- I. Is it possible to reproduce state-of-the-art threshold measurements as good or better than those produced by commercially-available dark-adaptometers and reported in the literature?
- II. Do the threshold measurements in the elderly compare with literature data adjusted to exclude aged crystalline lens and pupillary miosis contributions?
- III. Are test results from the novel light-emitting system repeatable?
- IV. If the results are not repeatable, can any assumption be made about reducing their variability through software and/or hardware optimisation of the novel light-emitting system?

V. Is the novel light-emitting system comfortable and easy to use by normal healthy adults despite age differences?

4. Method

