4.1. Study design

Single-centre, observational healthy case-only study.

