4.4. Participants

Healthy adult volunteers with no prior or current eye problems and good general health will be recruited from University of Liverpool students and staff, Royal Liverpool University Hospital students, and people accompanying patients attending St. Paul's Eye Unit.

Two age-groups of subjects will be enrolled:

Group 1: 10 people aged 18 to 40

Group 2: 10 people aged 50 to 70

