4.11. Primary outcomes

Primary outcome variables for Group 1&2:

- Rod-cone break
- Absolute threshold

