4.13. Data collection/Project management

Anonymised data will be collected by the PI and stored in accordance with the Data Protection Act and data governance protocols of the University of Liverpool and Royal Liverpool University Hospital. A clinical database will be arranged by the PI and held for a period between 6-12 months into a locally installed electronic data recording system at the Clinical Eye Research Centre of St. Paul's Eye Unit, Royal Liverpool University Hospital.

A Project Steering Committee will meet at the beginning and at the end of the investigation. In addition to these meetings they will be issued with information about the real-time data collected by the PI when all recruited participants will have undergone at least one dark-adaptometry testing visit. The committee will evaluate system performance and variability of collected data based on the real-time plots recorded by the PI during the first dark-adaptometry visit. In the event that the assumptions underlying the sample size calculation are seen to be incorrect at the time of the interim analysis, they will have the option to advise further recruitment to the study.

Data variables:

Refractive error (-5÷0÷5 dioptres – spherical; 0÷3 – cylinder)

DVA (letters)

Low-luminance NVA (letters)

Contrast sensitivity (letters)

Pupil size (mm)

Visual field

Fundus

Data collected during the dark-adaptometry testing visits will be in the form of a “log threshold intensity vs time” plot together with a .csv file including a list of the data points.

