Cone- and rod-mediated parameters were compared to previous literature on human dark adaptation to evaluate the performance of the developed dark adaptometer. Clinical data reported in [6] were particularly taken into consideration since a similar DA protocol was used by Jackson et al. to assess dark adaptation changes with age and as a function of decade. In addition, trial outcomes of interest were the test-retest and usability score results and variability obtained from participants after one or multiple DA visits.

Repeatability coefficient (RC) and within-case coefficient of variance (wCV) were calculated starting from the within-subject variance for each trial participant who completed at least 2 DA visits in order to assess variation in repeat measurements on the same patient. Intra-class correlation coefficient (ICC) – 2-way mixed-effects, absolute agreement, average measurement – was calculated for both

Group 1 and Group 2 through SPSS® Statistics V22.0 (IBM, Armonk, USA) to obtain the proportion of total variation in measurements by between-patient differences.

A pen-and-paper questionnaire as in Appendix 1-a was presented to participants twice on completion of the first and the third DA appointment. Seventeen questions targeting hardware and software implementation as well as personal feedback on the duration of the DA test were asked to rate comfort and ease of use of the developed system.

- [1] Alpern M. et al. Rhodopsin kinetics in the human eye. *Journal of Physiology*, 217 (1971), pp. 447-471.
- [2] W.A.H. Rushton, D.S. Powell. The rhodopsin content and the visual threshold of human rods. *Vision Research*, 12 (1972), pp. 1073–1081.
- [4] T.D. Lamb. Spontaneous quantal events induced in toad rods by pigment bleaching. *Nature*, 287 (5780) (1980), pp. 349-351.
- [5] T.D. Lamb. The involvement of rod photoreceptors in dark adaptation. *Vision Research*, 21 (12) (1981), pp. 1773-1782.

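### Question I asks whether the device is as good as or better than commercial adaptometers, but the only planned comparison is an informal one with published values, which cannot support either conclusion

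*Protocol*

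**What the plan says.** Question I appears in the Project Summary (section 1) and again under Aim (section 3). It asks whether the device can reproduce thresholds "as good or better than those produced by commercially-available dark-adaptometers", and continues so as to include values reported in the literature.

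The design is a "Single-centre, observational healthy case-only study". The participants are "20 healthy volunteers", split in section 4.4 as "Group 1: 10 people aged 18 to 40" and "Group 2: 10 people aged 50 to 70". Neither the procedures (4.7) nor the schedule (4.9) lists a second adaptometer. Section 4.11, under "Primary outcome variables for Group 1&2", names rod-cone break and absolute threshold.

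Section 4.14 of the protocol says who analyses and reviews the data, but gives no method. The SAP says that the fitted cone and rod parameters are "compared to previous literature on human dark adaptation to evaluate the performance of the developed dark adaptometer". It singles out one ageing study because that study's test protocol was similar. It also plans a repeatability coefficient (RC), a within-case coefficient of variance (wCV) and an intra-class correlation (ICC).

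**The concern.** The words *as good* express an equivalence or non-inferiority idea, and *better* a superiority idea. Each needs a defined difference, a statement of its uncertainty, and a comparison that isolates the device. The plan supplies none of these. Nothing fixed in advance could contradict a statement that the results look like the literature, so anything short of a gross discrepancy could be reported as a positive answer to the first research question.

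The stakes are in the wording of the conclusion. The Background already anticipates that the device will compare well with conventional instruments and be used by high-street optometrists. A claim against commercial devices would go further than these data can.

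**Working it through.** The plan states no figure for this comparison that could be reproduced. The group sizes add up (10 + 10 = 20), but no SD, margin, alpha or power appears in the available text. The check therefore has a design part and a precision part in SD units.

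**Design: what can be separated?**

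- The end of the Background says that the intensity, duration, colour, area and location of the fixation, bleach and target lights all affect measured thresholds. It gives this as the reason for adopting the published staircase procedure.
- Sharing the staircase aligns the method of finding a threshold. It does not make the goggles' display, the camera-flash bleach or the volunteers the same as those behind the published values.
- Question II recognises a population effect too, since it asks for literature data adjusted for the ageing lens and small pupil.
- A difference from a published mean therefore mixes device, stimulus, bleach and population, and so does the absence of a difference. More participants would narrow the interval but would not separate these sources.
- The comparator itself is unclear. The Background says that the benchmark instrument is no longer sold, and neither document says that the main reference data came from a commercially available device.

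**Precision: how wide would an interval be?**

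Input: n = 10 per group (section 4.4). Assumptions: two-sided 95% CI, normal data, one value per person.

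1. Published mean treated as fixed: half-width = t(0.975, n−1)/√n = 2.262/3.162 = **0.715 SD**.
2. Published mean from m people with a common SD: half-width = t(0.975, n+m−2) × √(1/n + 1/m). The documents do not give m, so a range is shown:
   - m = 10: 2.101 × 0.4472 = **0.94 SD**
   - m = 20: 2.048 × 0.3873 = **0.79 SD**
   - m = 50: 2.002 × 0.3464 = **0.69 SD**

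   The last value is slightly below the fixed-mean result because the common-SD assumption raises the degrees of freedom from 9 to 58.
3. Repeatability: 10 people × (3 visits − 1) = 20 degrees of freedom within a group. The 95% CI for the within-subject SD, and so for an RC proportional to it, runs from √(20/34.17) = **0.77** to √(20/9.591) = **1.44** times the estimate. If everyone completed only the two visits that the SAP requires, there are 10 degrees of freedom and the factors are √(10/20.48) = 0.70 and √(10/3.247) = 1.75.

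The SAP provides for none of these intervals. It also names no RC, wCV or ICC for another device against which the new values could be set.

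**The case against.** The strongest reply is that Question I refers to published measurements, that it is a question with no formal hypothesis attached, and that a descriptive benchmark is reasonable in a 20-person first evaluation. Most of this stands. On that reading the lack of an on-site commercial device is no contradiction, and a descriptive comparison is worth making. What remains is that the protocol says it intends to answer the question, and the planned comparison cannot answer it as worded.

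Four stronger readings are tempting, but the documents do not support them.

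- *A biased device would usually pass.* With n = 10, a two-sided one-sample t-test has power 0.293 for a bias of 0.5 SD and 0.506 for 0.7 SD, so a reader might infer pass rates of 71% and 49%. The SAP specifies no significance test for this comparison, so these rates are not a property of the plan.
- *The comparison is wholly undefined.* The SAP gives two models, named parameters and a main reference study with the reason for choosing it. Only the difference measure, interval and criterion are missing.
- *Precision is ignored.* *As good or better* could mean precision, and RC, wCV and ICC are planned. They address repeatability (Question III) and could be set beside published values, but no such value is named.
- *The sample is simply too small.* Section 4.13 refers to a sample size calculation and lets the committee advise further recruitment ("In the event that the assumptions underlying the sample size calculation are seen to be incorrect at the time of the interim analysis"). The calculation is not in the available text, part of which was removed, so its absence is not held against the plan. The design limit would hold at any n.

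**Conclusion.** The point holds as a limit on what may be concluded. The study can describe how its thresholds sit against published ones. It cannot show that the device equals or surpasses commercially available adaptometers, because no concurrent device isolates the device effect and no difference, interval or criterion is specified.

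The design argument needs no numerical assumption. The size of the uncertainty, roughly 0.7 to 0.9 SD either side of a group's mean difference, is illustrative. It rests on 10 people per group, assumed reference sizes of 10 to 50 and a common SD, and cannot be turned into minutes or log units because the documents give no SD. It is a change that should be made; the study remains worth doing without it.

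**What to change.** - **Protocol, sections 1 and 3:** reword Question I as agreement with published values, dropping *or better* and *commercially-available*.
- **SAP:** for each primary outcome (rod-cone break in minutes, absolute threshold in log units) and each age group, state the published reference value. Report the mean difference from it with a 95% CI that includes the published value's own uncertainty where available.
- **SAP, repeatability:** report 95% CIs for RC, wCV and ICC.
- **Interpretation:** describe the differences. Say that the device agrees only if a limit, justified separately on each outcome's own scale, was fixed beforehand; otherwise make no such statement.
- **A limit to avoid:** the 0.3 log decrement in section 4.8 should not serve as a general limit. It is a step size in the psychomotor test with no stated link to acceptable agreement, and it cannot apply to rod-cone break, which the SAP defines in minutes, or to cone time constants or slopes.

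The cost is a more modest claim and slightly more analysis output, with no extra participants, visits or devices. A true claim of *as good or better* would need the same people measured on a second adaptometer, which would be a different study.
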